## NON-INTERVENTIONAL STUDY PROTOCOL SYNOPSIS

Name of company/Marketing Authorisation Holder: Boehringer Ingelheim		Tabulated Study Protocol	
Name of finished product: JARDIANCE® Tablets			
Name of active ingredient: Empagliflozin			
Protocol date: 10 APR 2015	Trial number: 1245.94		Revision date:
Title of study:		Post Marketing Surveillance in Japan on Long Term Drug Use of JARDIANCE® Tablets in Patients with type 2 Diabetes Mellitus	
Co-ordinating Investigator :		Not applicable	
Study site(s) :		1,300 in Japan	
Clinical phase:		IV	
Objectives:		To investigate the safety and efficacy of long-term daily use of JARDIANCE® Tablets in Japanese patients with type 2 diabetes mellitus.	
Methodology:		Non-interventional, prospective, observational	
No. of patients:			
Total entered:		3,000 patients with the assessment of 3-year completed administration	
each treatment:			
Diagnosis:		Type 2 diabetes mellitus	
Main criteria for inclusion:		Male and female Japanese patients with type 2 diabetes mellitus who have never been treated with JARDIANCE® Tablets before the enrolment.	
Test product(s) :		JARDIANCE® Tablets	
dose:		10 mg, 25 mg	
mode of admin. :		Oral	
Comparator product(s):		Not applicable	
dose:		Not applicable	
mode of admin. :		Not applicable	
Duration of treatment:		156 weeks	

**1245.94**

**Observational plan**

**c02153926-02**

Proprietary confidential information © 2015 Boehringer Ingelheim International GmbH or one or more of its affiliated companies

Name of company/Marketing Authorisation Holder: Boehringer Ingelheim		Tabulated Study Protocol	
Name of finished product: JARDIANCE® Tablets			
Name of active ingredient: Empagliflozin			
Protocol date: 10 APR 2015	Trial number: 1245.94		Revision date:
Criteria for efficacy:	Primary efficacy endpoint: None Secondary efficacy endpoint: Change from baseline in HbA1c and FPG to the last- observation on treatment.		
Criteria for safety:	Primary safety endpoint: Incidence of adverse drug reactions (ADRs)		
Statistical methods:	Descriptive statistics will be summarised for safety and efficacy. A mixed model repeated measures analysis will be performed for HbA1c over time.		

## FLOW CHART

	Screening	Treatment	End of Trial
Observation period*	Before first administration of JARDIANCE® Tablets	12, 26, 40, 52, 64, 78, 104, 130 W	156 W 
Registration	X 		
Demographics	X		
Administration of JARDIANCE® Tablets		X	X
Medical History/ Concomitant disease	X		
Waist circumference	X		
Blood pressure pulse rate and ECG	X	X	X
HbA1c and fasting plasma glucose	X	X	X
Laboratory tests	X	X	X
Physical examination (Body weight, height)	X	X 	X 
12-lead ECG	X	X	X
Pregnancy status 	X	X	X
Concomitant drug(s) and antidiabetic therapy 	X	X	X
Adverse events ██████████		X	X

W: Weeks

\*: Time points during the observation period are approximate. Collected data should be reported as of the closest available visit.

1: Patients administered JARDIANCE® Tablets will be registered preferably within 14 days from the day of first administration.

2: Body weight only

3: Only for female patients

4: From 1 month before first administration of JARDIANCE® Tablets

5: Time point for 156 weeks should be more than 1092 days.

Electronic case report form (eCRF): At 12 weeks, 52 weeks, 104 weeks, 156 weeks or discontinuation and each time when an adverse event has occurred, data in corresponding observation period should be entered into eCRF and transmitted using the EDC system.

## ABBREVIATIONS

ADR	Adverse drug reaction
AE	Adverse Event
ALP	Alkaline phosphatase
ALT	Alanine aminotransferase
AMY	Amylase
AST	Aspartate aminotransferase
BI	Boehringer Ingelheim
BICMQ	Boehringer Ingelheim customised MedDRA query
BMI	Body-mass index
BUN	Blood Urea Nitrogen
CK	Creatine Kinase
CRF	Case Report Form
DEDP	Drug Exposure During Pregnancy
ECG	Electrocardiogram
EDC	Electronic Data Capture
eGFR	Estimated Glomerular filtration Rate
FPG	Fasting plasma glucose
$\gamma$ -GTP	Gamma-glutamyl-transferase
GPSP	Good Post-marketing Study Practice
GVP	Good Vigilance Practice
HDL	High Density Lipoprotein cholesterol
IRB	Institutional Review Board
J-PAL	Japanese Pharmaceutical Affairs Law
LDH	Lactic dehydrogenase
LDL	Low Density Lipoprotein cholesterol
LIP	Lipase
MedDRA	Medical Dictionary for Regulatory Activities
MHLW	Ministry of Health, Labour and Welfare
MMRM	Mixed model repeated measures
NGSP	National Glycohemoglobin Standardization Program
NYHA	New York Heart Association
MR	Medical Representative
PMDA	Pharmaceuticals and Medical Devices Agency
PMS	Post Marketing Surveillance
REML	Restricted maximum likelihood
SAE	Serious Adverse Event
SGLT-2	Sodium-dependent glucose co-transporter-2
SMQ	Standardised MedDRA Queries
SOP	Standard Operating Procedure
T-BIL	Total Bilirubin
T-CHO	Total Cholesterol
TG	Triglycerides
UA	Uric Acid

**1245.94**

**Observational plan**

**c02153926-02**

---

Proprietary confidential information © 2015 Boehringer Ingelheim International GmbH or one or more of its affiliated companies

ULN

Upper Limit of Normal range

## **1. INTRODUCTION**

### **1.1 MEDICAL BACKGROUND**

The estimated worldwide prevalence of diabetes in 2011 was 366 million with an increase of 50% expected within the next 20 years. Most of these patients have type 2 diabetes mellitus, which is characterised by insulin resistance and impaired insulin secretion. Diabetes is associated with microvascular complications and elevated cardiovascular risk. Treatment of type 2 diabetes usually involves lifestyle interventions such as diet and exercise, as well as the administration of oral or injectable antidiabetic drugs. Although initially effective, currently available oral antidiabetic agents often fail to maintain long-term glycaemic control or are associated with side effects that may limit their use. Hence, there is a need for new therapeutic options for patients with type 2 diabetes to provide sustained improvements in glycaemic control and to contribute to reducing cardiovascular risk factors such as overweight and hypertension.

The kidney has a role in the regulation of blood glucose levels and can therefore serve as a target for new antidiabetic drugs. The sodium-dependent glucose co-transporter-2 (SGLT-2) is mainly expressed in the renal proximal tubules and accounts for approximately 90% of renal glucose reabsorption. Inhibition of SGLT-2 decreases the renal reabsorption of glucose, thereby promoting glucose excretion in the urine with a resulting reduction in blood glucose levels. Due to their insulin-independent mechanism of action, SGLT-2 inhibitors have a low risk of hypoglycaemia. Further benefits of SGLT-2 inhibition may include weight reduction due to the calorie loss associated with increased glucose excretion and a decrease in blood pressure that is possibly due to a mild diuretic effect.

### **1.2 DRUG PROFILE**

Empagliflozin (internal code: BI 10773) is a novel, orally administered, potent, and selective SGLT-2 inhibitor developed by Boehringer Ingelheim. Empagliflozin is proposed to be registered for treatment of type 2 diabetes mellitus in conjunction with diet and exercise, as monotherapy or as add on other oral antidiabetic treatments or insulin. Empagliflozin tablets are to be administered once daily, with or without food. The recommended therapeutic dose is 10 mg. If treatment efficacy is insufficient, the daily dose can be increased to 25 mg once daily while the patient's condition is being carefully monitored.

## **2. RATIONALE, OBJECTIVES, AND BENEFIT-RISK ASSESSMENT**

### **2.1 RATIONALE FOR PERFORMING THE STUDY**

In Japan, post-approval execution of post marketing surveillance (PMS) is requested by the Japanese Pharmaceutical Affairs Law (J-PAL) in order to accumulate safety and efficacy data for re-examination. Re-examination period is defined by J-PAL. New integrant is 8 years for re-examination. Eight years after approval of a new substance, results of PMS need to be submitted as a part of re-examination dossier to the Japanese regulatory authority, the Ministry of Health, Labour and Welfare (MHLW).

Collected data from PMS will be included in the Japanese periodic safety reports and submitted to MHLW on designated dates until the end of re-examination period.

The protocol may be revised because of new information or knowledge obtained in the course of conducting PMS. When a change of the approved label such as in dosage and administration or indications is made during the re-examination period of JARDIANCE® Tablets (except that for this change a re-examination period is newly designated by MHLW) and NBI finds it necessary to revise this protocol, handling each matter should be discussed and the protocol may be revised. If any issue or concern arises (e.g. suggestion of a potential for clinically significant adverse reaction, remarkable increase in incidence of an adverse reaction, or any issue or concern on safety or efficacy assessment made prior to the approval of JARDIANCE® Tablets) in the course of PMS, implementation of additional special surveillance or post-marketing clinical trial should be discussed to identify or confirm a cause or estimated cause of such issue. Special surveillance is defined by J-PAL. It means surveillance for long-term use or special patient population (elderly, renal/hepatic dysfunction etc.).

SGLT-2 inhibitor is a drug class with a new mode of action, and does not comprise sufficient Japanese safety data within the class. It's not that there is a particular safety issue concerning JARDIANCE®; however, further surveillance is needed to monitor possible increase in the incidence of malignant tumor which is potentially associated with drugs of the same class, as well as the effect on kidneys attributable to its mode of action by which a long-term use stimulates the urinary excretion of glucose, and also the effect on hepatic function and bone metabolism.

This long-term drug use surveillance is planned to collect and investigate primarily safety data.

### **2.2 STUDY OBJECTIVES**

Study objectives are to investigate the safety and efficacy of long-term daily use of JARDIANCE® Tablets in patients with type 2 diabetes mellitus.

### **2.3 BENEFIT-RISK ASSESSMENT**

In this non-interventional PMS, marketed products will be used. ADRs as risk of JARDIANCE® Tablets are listed in package insert.

### 3. DESCRIPTION OF DESIGN AND STUDY POPULATION

#### 3.1 OVERALL DESIGN AND PLAN

This PMS is a prospective study using a continuous investigation system. Patients with type 2 diabetes mellitus will be included in the surveillance. No specific criteria (e.g., demographics, baseline characteristics, concomitant drugs in use) are defined for patient enrolment.

[figure not shown]
Patients administered JARDIANCE® Tablets will be registered preferably within 14 days from the day of first administration. Patients will be observed for up to 156 weeks (approximately 36 months) after start of the treatment with JARDIANCE® Tablets or at premature discontinuation and dropout. Observations are made at the following time points: before first administration of JARDIANCE® Tablets (screening, this visit is defined as baseline) and 12, 26, 40, 52, 64, 78, 104, 130 and 156 weeks after the start of treatment, or at discontinuation.

There are 4 separate eCRFs for 0-12 (Book 1), 13- 52 (Book 2), 53- 104 (Book 3) and 105-156 weeks (Book 4).

[figure not shown]
At 12, 52, 104 and 156 weeks after the start of treatment or at discontinuation, data are to be transmitted immediately after entered into eCRF. In case of occurrence of any adverse events, data in corresponding observation period should be immediately entered into eCRF and transmitted.

##### 3.1.1 Administrative structure of the study

[figure not shown]

**3.2 DISCUSSION OF STUDY DESIGN, INCLUDING THE CHOICE OF CONTROL GROUP(S)**

This is a non-interventional, observational study based on newly collected data under routine medical practice. There is no control group.

**3.3 SELECTION OF POPULATION**

Total number of entered patients is 3,000 patients with the assessment of 3-year completed administration.

No limitations are set up on background factors of patients and their concomitant drugs in use of actual medical practice.

Estimated number of enrolled patients with renal dysfunction ( $45 \text{ mL/min/1.73m}^2 \leq \text{eGFR} < 60 \text{ mL/min/1.73m}^2$ ) is 100.

Grades for renal dysfunction are as follows.

Normal:  $\text{eGFR} \geq 90 \text{ mL/min/1.73m}^2$   
Mild:  $\text{eGFR} \geq 60 \text{ mL/min/1.73m}^2$  and  $< 90 \text{ mL/min/1.73m}^2$   
Moderate:  $\text{eGFR} \geq 30 \text{ mL/min/1.73m}^2$  and  $< 60 \text{ mL/min/1.73m}^2$   
Severe:  $\text{eGFR} < 30 \text{ mL/min/1.73m}^2$

Estimated number of enrolled elderly patients ( $\geq 75$  years) is 100.

Estimated number of enrolled patients with hepatic dysfunction is 100.

Patients with hepatic dysfunction: Investigator judgment is moderate or severe.

Investigator should judge the grade for hepatic dysfunction by using lab data category as described below and symptoms/concomitant diagnoses.

Normal: Normal AST/ALT  
Mild: AST/ALT >ULN and <3x ULN  
Moderate: AST/ALT ≥3xULN and <5x ULN + total Bil ≤ 2xULN  
Severe: AST/ALT ≥5 xULN, or AST/ALT ≥3xULN and <5x ULN + total Bil > 2xULN  
ULN is taken from the corporate standard reference range (001-MCG-157\_RD-01: Standard Ranges).

Sites throughout entire country will be equally listed according the size of the hospitals or general clinics at which JARDIANCE® Tablets are available for prescription.

Expected number of patients per site is 5-30 patients. Patients will be selected by using the continuous investigation system. The continuous investigation system is commonly used in Japanese PMS and accepted as a patient selection process by the PMDA.

Continuous investigation system is a method of registration that the investigator enrolls the patients who will start administration of marketed product into the PMS continuously (without exception) until the requested number of patients is reached.

Preferably, investigators will register patients within 14 days including the day on which the administration of JARDIANCE® Tablets is started. However, patients who are registered over 15 days after starting administration of JARDIANCE® Tablets are also used for safety and efficacy analysis.

The registered patients: The patient registration date are entered into eCRF and transmitted using the EDC system.

The entered patients: The patient are registered and observational data after taking JARDIANCE® Tablets are entered into eCRF and transmitted using the EDC system.

Investigators will confirm the continuous registration at the site at the end of the enrolment period with the signed form.

### **3.3.1 Main diagnosis for study entry**

The PMS is performed in patients with type 2 diabetes mellitus.

### **3.3.2 Inclusion criteria**

Patients with type 2 diabetes mellitus who have never been treated with JARDIANCE® Tablets / Empagliflozin before enrollment will be included.

### **3.3.3 Exclusion criteria**

None

### **3.3.4 Removal of patients from therapy or assessments**

#### **3.3.4.1 Removal from individual patients**

Patients may voluntarily discontinue the treatment under study for any reason. Patients may also discontinue the PMS if the investigator judges that the patient is no longer able to participate for any medical reason (pregnancy, surgery, adverse events, or other disease).

#### **3.3.4.2 Discontinuation of the study by the sponsor**

NBI reserves the right to discontinue the PMS overall or at a particular PMS study site at any time for the following reasons:

1. Failure to meet expected enrolment overall goals or goals at a particular study site,
2. Emergence of any efficacy/safety information that could significantly affect continuation of the PMS,
3. Violation of Good Post-marketing Study Practice (GPSP) or the contract of a study site or investigator, thereby disturbing the appropriate conduct of the PMS.

The investigator / the PMS site will be reimbursed for reasonable expenses incurred as a result of PMS termination (except in case of the third reason).

## **4. TREATMENTS**

### **4.1 PRESCRIBED TREATMENTS TO BE OBSERVED**

#### **4.1.1 Identity of test product(s) and comparator product(s)**

In this non-interventional PMS, marketed products will be used. There will be no investigational products in this PMS. It is solely in the decision of the investigator to initiate JARDIANCE® Tablets.

#### **4.1.2 Method of assigning patients to treatment groups**

There is no randomisation, since this is an observational surveillance study.

#### **4.1.3 Selection of doses in the study**

The usual dose is 10 mg of a JARDIANCE® Tablet administered orally once daily. If treatment efficacy is insufficient, the daily dose can be increased to 25 mg once daily while the patient's condition is being carefully monitored.

#### **4.1.4 Drug assignment and administration of doses for each patient**

The investigators indicate doses and timing based on the package insert.

### **4.2 CONCOMITANT THERAPY, RESTRICTIONS, AND RESCUE TREATMENT**

#### **4.2.1 Rescue medication, emergency procedures, and additional treatment(s)**

There are no special emergency procedures to be followed stipulated by the protocol. It is solely the responsibility of the investigator to initiate such measures according to local clinical practice.

#### **4.2.2 Restrictions**

##### **4.2.2.1 Restrictions regarding concomitant treatment**

All the restrictions listed in the package insert are applied.

##### **4.2.2.2 Restrictions on diet and life style**

All the restrictions listed in the package insert are applied.

### **4.3 TREATMENT COMPLIANCE**

The investigators advise patients to take the prescribed product correctly and verbally confirm compliance to treatment medications at every patient visit.

## 5. VARIABLES AND THEIR ASSESSMENT

### 5.1 EFFICACY

#### 5.1.1 Endpoint(s) of efficacy

There is no primary endpoint for efficacy as the primary objective of a PMS is evaluating safety (See Section 5.2).

The secondary endpoint for this PMS is the change from baseline in HbA1c and FPG at the last observation during the observation period.

#### 5.1.2 Assessment of efficacy

##### *HbA1c:*

The blood samples can be taken at any time and will be measured at the sites by using National Glycohemoglobin Standardization Program (NGSP).

##### *Fasting plasma glucose (FPG):*

Fasting is defined as before breakfast and more than 10-hr past from previous JARDIANCE® Tablets administration. The blood samples should be taken before breakfast and before JARDIANCE® Tablets administration. The blood samples will be taken and measured at the sites. Plasma glucose will be reported in mg/dL.

### 5.2 SAFETY

#### 5.2.1 Endpoint(s) of safety

Primary endpoint of this study is the number of patient with adverse drug reactions (ADRs)

The other safety endpoint is the number of patient with serious adverse events (SAEs) [REDACTED]

## 5.2.2 Management and reporting of adverse events/adverse reactions

### 5.2.2.1 Definitions of adverse events

#### Adverse event

An adverse event (AE) is defined as any untoward medical occurrence in a patient or clinical investigation subject administered a medicinal product and which does not necessarily have a causal relationship with this treatment. An adverse event can therefore be any unfavorable and unintended sign (e.g. an abnormal laboratory finding), symptom, or disease temporally associated with the use of a medicinal product, whether or not considered related to the medicinal product.

#### Adverse drug reaction

An adverse drug reaction is defined as a response to a medicinal product which is noxious and unintended. Response in this context means that a causal relationship between a medicinal product and an adverse event is at least a reasonable possibility. Adverse reactions may arise from use of the product within or outside the terms of the marketing authorisation or from occupational exposure. Conditions of use outside the marketing authorization include off-label use, overdose, misuse, abuse and medication errors.

#### Serious adverse event

A serious adverse event is defined as any AE which

- results in death,
- is life-threatening,
- requires in-patient hospitalization, or
- prolongation of existing hospitalisation,
- results in persistent or significant disability or incapacity, or
- is a congenital anomaly/birth defect

Life-threatening in this context refers to a reaction in which the patient was at risk of death at the time of the reaction; it does not refer to a reaction that hypothetically might have caused death if more severe.

Medical and scientific judgment should be exercised in deciding whether other situations should be considered serious reactions, such as important medical events that might not be immediately life threatening or result in death or hospitalisation but might jeopardise the patient or might require intervention to prevent one of the other outcomes listed above. Examples of such events are intensive treatment in an emergency room or at home for allergic bronchospasm, blood dyscrasias or convulsions that do not result in hospitalisation or development of dependency or abuse. Any suspected transmission via a medicinal product of an infectious agent is also considered a serious adverse reaction.

An AE which possibly leads to disability will be reported as an SAE. Every new occurrence of cancer or an exacerbation of an existing cancer will be reported as a SAE regardless of the duration between discontinuation of the drug and the occurrence of the cancer.

#### Adverse Event of Special Interest (AESI)

The term AESI relates to any specific AE that has been identified at the project level as being of particular concern for prospective safety monitoring and safety assessment within this study, e.g. the potential for AEs based on knowledge from other compounds in the same class.

No AESIs have been defined for this study.

### **5.3 ADVERSE EVENT AND SERIOUS ADVERSE EVENT COLLECTION AND REPORTING**

#### **5.3.1 Adverse event and serious adverse event collection**

The investigator shall maintain and keep detailed records of all AEs in their patient files.

#### Collection of AEs

The study design is of non-interventional nature and the study is conducted within the conditions of the approved marketing authorisation. Sufficient data from controlled interventional trials are available to support the evidence on the safety and efficacy of the studied BI drug. For this reason the following AE collection and reporting requirements have been defined.

The following must be collected by the investigator in the (e)CRF from first intake of JARDIANCE® Tablets at baseline visit and within 7 days (inclusive) after the last intake:

- all ADRs (serious and non-serious) as soon as possible,
- all AEs with fatal outcome in patients exposed to JARDIANCE® Tablets as soon as possible,

All ADRs, including those persisting after study completion must be followed up until they are resolved, have been sufficiently characterized, or no further information can be obtained.

The investigator carefully assesses whether an AE constitutes an ADR using the information below.

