- Continuation of the event despite the withdrawal of the medication, taking into account the pharmacological properties of the compound (e.g. after 5 half-lives). Of note, this criterion may not be applicable to events whose time course is prolonged despite removing the original trigger. Additional arguments amongst those stated before, like alternative explanation (e.g. situations where other drugs or underlying diseases appear to provide a more likely explanation for the observed event than the drug concerned).

- Disappearance of the event even though the study drug treatment continues or remains unchanged.

Intensity of adverse event

The intensity of the AE should be judged based on the following:

Mild: Awareness of sign(s) or symptom(s) which is/are easily tolerated  
Moderate: Enough discomfort to cause interference with usual activity  
Severe: Incapacitating or causing inability to work or to perform usual activities

Pregnancy:

In rare cases, pregnancy might occur in a study. Once a patient has been enrolled into the PMS, after having taken JARDIANCE® Tablets, the investigator must report any drug exposure during pregnancy which occurred in a female patient or in a partner to a male patient to the Sponsor by means of Part A of the Pregnancy Monitoring Form. The outcome of the pregnancy associated with the drug exposure during pregnancy must be followed up and reported by means of Part B of the Pregnancy Monitoring Form.

In the absence of a reportable AE, only the Pregnancy Monitoring Form must be completed.

Expedited Reporting of AEs and Drug Exposure During Pregnancy

The following must be reported by the investigator to the Sponsor's unique entry point from first intake of JARDIANCE® Tablets at baseline visit and within 7 days (inclusive) after last intake:

Type of Report	Timeline
All SA DRs associated with the JARDIANCE ® Tablets	As soon as possible
All A Es with fatal outcome in patients exposed to JARDIANCE ® Tablets	As soon as possible
All non-serious ADRs associated with the JARDIANCE ® Tablets	As soon as possible
All pregnancy monitoring forms	As soon as possible

The same timelines apply if follow-up information becomes available for the respective events. In specific occasions the Investigator could inform the Sponsor upfront via telephone. This does not replace the requirement to complete the appropriate (e)CRF.

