**6.2.2 Treatment period(s)**

Treatment period(s) 12, 26, 40, 52, 64, 78, 104 and 130 weeks after the start of treatment When stop the treatment, please complete the EOT visit instead.	
Vital signs	Blood pressure and pulse rate.
Body weight	Document body weight
Pregnancy status	Document when pregnancy is discovered.
ECG	Resting 12-lead ECG will be performed if applicable.
Laboratory tests	Haematology, Biochemistry, Urinalysis (see section 5.3.3 for minimum assessments).
Concomitant drugs and antidiabetic therapies	Document indication, start and stop date of each concomitant drugs and antidiabetic therapies.
Administration	Document dose, start and stop date and reason of termination.
Adverse events ██████████	Document details of any new AEs and obtain any new information about AEs ongoing at the last visit. ██████████ ██████████ ██████████

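### The protocol's instructions disagree on which adverse events and cancers sites must submit, so completeness of the all-causality AE, SAE and malignancy counts is not assured

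*Protocol*

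**What the plan says.** **Narrower text.** Protocol 5.3.1 (Collection of AEs) names two items that must go into the eCRF: "all ADRs (serious and non-serious) as soon as possible", and fatal AEs of any causality. It introduces them by noting that controlled trials already supply enough evidence, and continues: "For this reason the following AE collection and reporting requirements have been defined". The expedited-reporting table in 5.3.1 has the same scope plus pregnancy forms, and its window also closes "within 7 days (inclusive) after last intake".

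**Wider text.**
- Flow Chart, eCRF note: "each time when an adverse event has occurred, data in corresponding observation period should be entered into eCRF".
- Section 3.1: "In case of occurrence of any adverse events, data in corresponding observation period should be immediately entered into eCRF and transmitted".
- Sections 6.2.2 and 6.2.3, at each visit and at end of trial: "Document details of any new AEs and obtain any new information about AEs ongoing at the last visit". Neither names the eCRF.
- Section 8.3.1 lists adverse events and, separately, serious adverse events among the eCRF data to be drawn from source documents.

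**Cancer.** Section 5.2.2.1: "Every new occurrence of cancer or an exacerbation of an existing cancer will be reported as a SAE", and this applies "regardless of the duration between discontinuation of the drug and the occurrence of the cancer".

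**Analysis.** Section 5.2.1 makes the number of patients with SAEs a safety endpoint, not restricted to related events. SAP 7.8.1 tabulates AEs of any causality beside ADRs. Protocol 7.3.3 and SAP 6.1 set a 7-day analysis window for AEs.

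**The concern.** The all-causality tables need every AE, but a site working from 5.3.1 could reasonably leave out a non-fatal event it judged unrelated. The reason given in 5.3.1 for its list suits a reduced set, and the same section speaks of reportable AEs, which implies that some are not reportable. If sites differed in which section they followed, a low SAE or discontinuation count could reflect what was submitted and not what happened.

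Cancer matters most here, because 2.1 names malignant tumour as a reason for the surveillance. The causality guidance in 5.3.1 gives a cancer diagnosis within days or weeks of administration as an argument against a causal relationship. That points early cancers towards the unrelated category, which is off the 5.3.1 list unless fatal. Later cancers are due under 5.2.2.1 but fall outside the 5.3.1 windows.

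**Working it through.** **1. The plan's own figure.** Section 7.6 gives the chance of at least one ADR among 3,000 completers, 1 − (1 − p)^3000.
- p = 0.10%: 1 − 0.999^3000 = 95.03% (stated 95%).
- p = 0.16%: 1 − 0.9984^3000 = 99.18% (stated 99%).

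Both reproduce. The statement concerns ADRs, which every section requires, so it is little affected.

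**2. Which events are in dispute.** Section 5.3.1 counts unknown causality as an ADR. Within the 7-day window, investigator causality and outcome give four classes:

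| Investigator causality | Fatal | Non-fatal |
|---|---|---|
| ADR (high, low or unknown) | on the 5.3.1 list | on the list |
| Unrelated | on the list | not on the list |

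Three of the four are required under any reading. The fourth depends on how 5.3.1 is read beside the wider text.

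**3. Which outputs use that class.** SAP 7.8.1 lists 8 tables by SOC and PT: 4 for ADRs and 4 for all causality. The all-causality death table is covered by the fatal-AE rule, so 4 − 1 = 3 are affected: AEs, serious AEs, and AEs leading to discontinuation. Add the overall summary, the intensity table, the AE-based risk-item summaries, and the subgroup serious-AE summaries (produced only if a subgroup difference is significant): 3 + 1 + 1 + 1 + 1 = 7 output types.

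**4. Does the safety-database merge close the gap?** SAP 7.8.1 merges CRF data with the local safety database. The stated duty to report to the sponsor has the same scope as the CRF list, so the merge is not shown to supply the missing class. The same limit reaches ADRs that only the sponsor judges related (7.3.3, SAP 7.8.1), since the sponsor must first receive the event.

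**5. Cancer.** One rule (5.2.2.1) sets no limit on causality or time. Two collection or reporting windows (the 5.3.1 list and the expedited table) stop at 7 days. Protocol 7.3.3 and SAP 6.1 are analysis windows: they do not bar collection, but they place later cancers outside the main AE analysis. Section 6.1 ends the PMS at week 156 or the last visit before discontinuation, so nothing visible plans a search for later cancers.

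**6. Size, illustration only.** Let u be the share of all SAEs that are non-fatal and judged unrelated, and c the fraction of those that sites submit. The documents give neither. The recorded share of SAEs is 1 − u(1 − c).

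| | c = 0 | c = 0.5 | c = 0.9 | c = 1 |
|---|---|---|---|---|
| u = 0.3 | 70% | 85% | 97% | 100% |
| u = 0.8 | 20% | 60% | 92% | 100% |

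The range is too wide to support an estimate.

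**7. Timing.** SAP Table 6.2:1 closes registration on 31 May 2017. Adding 1,092 days gives 27 May 2020, which is 148 days before the SAP date of 22 October 2020.

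**The case against.** The strongest reply is that 5.3.1 sets a minimum. The Flow Chart and 3.1 expressly require eCRF entry for any AE. Section 8.3.1 expects AEs and SAEs in the eCRF, and 7.3.3 has investigator and sponsor both assess AE causality, which presupposes that the sponsor receives AEs. A site following every section would record everything. The cancer sentence can be read as a specific exception to the general window. Analyses are descriptive, and the primary endpoint is ADRs.

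Much of this stands. A reader might infer that only ADRs and fatal AEs were collected and that the SAE and cancer counts are therefore too low. The documents do not support that: they show conflicting instructions, not missed events. Nor do four passages contradict the cancer rule, because two of the four 7-day windows only define analysis periods.

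What remains is that no visible text says whether the list is a limit or a minimum, or that the cancer rule overrides the window. The visible SAP tables carry no caveat. Some text is blacked out beside the AE rows of the Flow Chart, 6.2.2 and 6.2.3, and after the SAE endpoint in 5.2.1. The visible conflict does not depend on it, but that text might bear on the answer.

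**Conclusion.** The point holds in limited form. Completeness is not assured for non-fatal events the investigator judges unrelated, which feed the SAE endpoint and seven SAP output types (one conditional), or for cancers found more than 7 days after last intake. Within the window, non-fatal cancers judged unrelated fall in the same disputed class.

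The shortfall cannot be derived and may be zero. Investigator-judged ADRs, fatal AEs within 7 days and the sample-size statement are little affected. Sponsor-only ADRs depend on receipt of the event. The conclusion assumes that the blacked-out text does not settle the collection rule. The list of risk items in SAP 7.8.1 is not visible, so a malignancy table may already be planned. This should be fixed, because it changes what a low SAE or cancer count can support.

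**What to change.** 1. Reconcile the Protocol Flow Chart, 3.1, 5.2.2.1, 5.3.1 (collection list and expedited table), 6.2.2, 6.2.3 and 8.3.1 on event scope and time window. State in SAP 7.8.1 which collection rule the AE and SAE tables rest on.
2. Unless full collection is confirmed, footnote the affected all-causality outputs: *reported events; non-fatal events judged unrelated may not have been systematically collected*. Do not read low counts there as low incidence. Keep the primary conclusion on all ADRs as defined, by investigator or sponsor, with fatal AEs alongside.
3. Unless the list not visible in SAP 7.8.1 already does so, tabulate all reported malignancies regardless of causality, split into those within 7 days of last intake and those later, and by source (CRF or safety database). State that follow-up ends at week 156 or the last visit before discontinuation, so later cancers arrive only incidentally and support no incidence rate.

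The cost is one extra table on data already held and a less favourable footnote. Given the dates, reconciling the text mainly corrects the record. A query to sites for unreported SAEs and cancers is possible, because 5.3.1 has investigators keep records of all AEs in patient files. With 1,300 sites in the synopsis it would be real work and should stay optional.
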